3.2. Secondary Endpoints

The secondary objectives for each dose level in each study part will be evaluated by the following endpoints:

Part A.2

- Antibody response of the mRNA-1273.214 (50 µg) against the ancestral SARS-CoV-2 and against SARS-CoV-2 variants (including Omicron) by GMT and SRR at multiple time points after the mRNA-1273.214 booster dose

Part E

- Immune response of 100 µg mRNA-1273.213 against the ancestral SARS-CoV-2 and variants at all timepoints by GMT, geometric mean fold rise (GMFR), and SRR

Part F (Cohort 1 and 2)

- GMT ratio of mRNA-1273.529 and mRNA-1273 against the Omicron variant at selected timepoints post-boost
- SRR difference between mRNA-1273.529 against the Omicron variant and mRNA-1273 against the Omicron variant
- GMT ratio of mRNA-1273.529 and mRNA-1273 against the ancestral SARS-CoV-2 and other variants at selected timepoints post-boost
- SRR difference between mRNA-1273.529 against the ancestral SARS-CoV-2 and other variants and mRNA-1273 against the ancestral SARS-CoV-2 and other variants

Part G

Key secondary endpoint:

- SRR difference between mRNA-1273.214 against ancestral SARS-CoV-2 and mRNA-1273 against ancestral SARS-CoV-2 at Day 29 and Day 91

Secondary endpoints:

- GMT ratio of mRNA-1273.214 and mRNA-1273 against the Omicron variant at selected timepoints post-boost
- SRR difference between mRNA-1273.214 against the Omicron variant and mRNA-1273 against the Omicron variant at selected timepoints post-boost
- GMT ratio of mRNA-1273.214 and mRNA-1273 against the ancestral SARS-CoV-2 and other variants at selected timepoints post-boost
- SRR difference between mRNA-1273.214 against the ancestral SARS-CoV-2 and other variants and mRNA-1273 against the ancestral SARS-CoV-2 and other variants at selected timepoints post-boost

Part H

- GMT ratio of mRNA-1273.222 50 µg and mRNA-1273 50 µg against ancestral SARS-CoV-2 (and other variants) at selected timepoints post-boost
- SRR difference between mRNA-1273.222 50 µg and mRNA-1273 50 µg against ancestral SARS-CoV-2 and variants of concern at selected timepoints post-boost

3.3. Exploratory Endpoints

The common exploratory endpoints shared by all study parts (A.1, A.2, B, C, D, E, F, G, H and J) are the following:

- Laboratory-confirmed symptomatic or asymptomatic SARS-CoV-2 infection will be defined in participants:
 - Primary case definition per the P301 (COVE) study
 - Secondary case definition based on the CDC criteria: the presence of one of the CDC-listed symptoms (<https://www.cdc.gov/coronavirus/2019-ncov/symptoms-testing/symptoms.html>) and a positive reverse transcriptase polymerase chain reaction (RT-PCR) test on a respiratory sample
 - Asymptomatic SARS-CoV-2 infection is defined as a positive RT-PCR test on a respiratory sample in the absence of symptoms or a positive serologic test for anti-nucleocapsid antibody after a negative test at time of enrollment

The common exploratory endpoints shared by study parts A.1, A.2, B, C, D, E, F, G and H) are the following:

- Characterization of the SARS-CoV-2 spike genetic sequence of viral isolates and comparison with the vaccine sequence

Exploratory endpoints for each dose level unique to each study part are the following:

Part A.1

- Immune response of mRNA-1273.211 against ancestral SARS-CoV-2 and SARS-CoV-2 variants including B.1.351 at selected timepoints post-boost by GMT, GMFR and SRR

Part B

- Immune response of mRNA-1273 against the ancestral SARS-CoV-2 and against SARS-CoV-2 variants at selected timepoints post-boost by GMT, GMFR, and SRR

Part C

- Immune response of mRNA-1273.617.2 against the ancestral SARS-CoV-2 and against SARS-CoV-2 variants including B.1.617.2 at selected timepoints post-boost by GMT, GMFR, and SRR

Part D

- Immune response of mRNA-1273.213 against the ancestral SARS-CoV-2 and against SARS-CoV-2 variants including B.1.351 and B.1.617.2 at selected timepoints post-boost

Part F (Cohort 1 and 2)

- T-cell and B-cell response after the mRNA-1273.529 booster

Part G

- T-cell and B-cell response after the mRNA-1273.214 booster

Part J

- Antibody response of mRNA-1273.815 (50 µg) and mRNA-1273.231(50 µg) against SARS-CoV-2 variants by GMT, GMFR, and SRR at selected timepoints

4. Study Design

4.1. Overall Study Design

This is an open-label, Phase 2/3 study to evaluate the immunogenicity, safety, and reactogenicity of mRNA-1273.211 (Part A.1), mRNA-1273 (Part B and F), mRNA-1273.617.2 (Part C), mRNA-1273.213 (Part D and E), mRNA-1273.529 (Part F), mRNA-123.214 (Part G and Part A.2), mRNA-1273.222 (Part H), mRNA-1273.815 (Part J) and mRNA-1273.231 (Part J) vaccines.

Part A.1

Part A.1 will evaluate two dose levels (50 or 100 µg total mRNA content) of the mRNA-1273.211 vaccine administered as a single booster dose to adult participants of the mRNA-1273-P301 (COVE) study who have previously received 2 doses of mRNA-1273 as a primary series. Enrollment will begin with the 50 µg dose arm, followed by the 100 µg dose arm.

Part A.2

Part A.2 will evaluate the immunogenicity, safety, and reactogenicity of the mRNA-1273.214 vaccine administered as a second booster dose to adult participants of the mRNA-1273-P205 study who have previously received 2 doses of mRNA-1273 as a primary series and a first booster of (50 µg total mRNA content) of the mRNA-1273.211 in Part A.1 of this study.

Part B

Part B will evaluate a single dose of mRNA-1273 100 µg vaccine administered as a single booster dose to adult participants of the mRNA-1273-P301 (COVE) study who have previously received 2 doses of mRNA-1273 as a primary series. Enrollment will begin upon the completion of enrollment of Part A.1 of the study.

Part C

Part C will evaluate two dose levels (50 or 100 µg) of the mRNA-1273.617.2 vaccine administered as a single booster dose to adults who have previously received 2 doses of mRNA-1273 as a primary series in Study mRNA-1273-P301 (COVE) or under the EUA. Enrollment of the 100 µg dose arm will begin upon completion of enrollment of Part B of

the study and the 50 µg dose arm enrollment will begin after completion of the 100 µg dose level arm in both Part C and D.

Part D

Part D will evaluate two dose levels (50 or 100 µg) of the mRNA-1273.213 vaccine administered as a single booster dose to adults who have previously received 2 doses of mRNA-1273 as a primary series in Study mRNA-1273-P301 (COVE) or under the EUA. Enrollment of the 100 µg dose level arm will begin upon completion of enrollment of Part C 100 µg dose level arm of the study followed by the 50 µg dose arm, which may run in parallel with Part C 50 µg dose arm enrollment.

Part E

Part E will be enrolled at a single clinical study site and will evaluate a single dose of mRNA-1273.213 100 µg vaccine administered as a single booster dose to adult participants who have previously received 2 doses of any SARS-CoV-2 mRNA authorized vaccine as a primary series. Enrollment of Part E will begin upon completion of enrollment of Part C of the study and will run concurrently with Part D.

Part F

Part F will consist of two cohorts.

Cohort 1 will evaluate 50 µg of the mRNA-1273.529 vaccine administered as a single booster dose to adult participants who have previously received 2 doses of mRNA-1273 as a primary series.

Cohort 2 will evaluate 50 µg of the mRNA-1273.529 vaccine and 50 µg of the mRNA-1273 when administered as a second booster dose to adult participants who have previously received 2 doses of 100 µg mRNA-1273 as a primary series and 1 booster dose of 50 µg mRNA-1273.

Enrollment of the mRNA-1273.529 Cohort 1 will run in parallel with the mRNA-1273.529 in Cohort 2. Enrollment of the 50 µg mRNA-1273 arm in Cohort 2 will begin upon completion of enrollment of the mRNA-1273.529 Cohort 2 arm and may run in parallel with the enrollment of the mRNA-1273.529 Cohort 1 arm.

Part G

Part G will evaluate 50 µg of the mRNA-1273.214 vaccine administered as a second booster dose to adults who have previously received 2 doses of 100 µg mRNA-1273 as a primary series and a single booster dose of 50 µg mRNA-1273. Enrollment of the mRNA-1273.214 50 µg second boost arm will begin upon completion of enrollment of the mRNA-1273 50 µg arm in Cohort 2 of Part F. Enrollment of the mRNA-1273.214 50 µg second boost arm may run in parallel with the enrollment of the mRNA-1273.529 Cohort 1 arm of Part F.

Part H

Part H will evaluate 50 µg of the mRNA-1273.222 vaccine administered as a second booster dose to adults who have previously received 2 doses of 100 µg mRNA-1273 as a primary series and a single booster dose of 50 µg mRNA-1273.

Part J

Part J will evaluate mRNA-1273.815 (50 µg) and mRNA-1273.231 (50 µg) administered as a booster to adults who previously received a primary series of mRNA vaccine, a first booster dose of a monovalent mRNA vaccine, and a second booster dose of a bivalent mRNA vaccine against SARS-CoV-2. Participants will be randomized in a 1:1 ratio to receive either mRNA-1273.815 (50 µg) or mRNA-1273.231 (50 µg).

Overall, study parts A.1, B, C, and D will assess antibody response of a single booster dose of mRNA vaccines in each study part. Part E will assess a single booster dose in participants who previously received any SARS-CoV-2 mRNA authorized vaccine. Study Part F Cohort 1 will assess whether a single booster dose of the mRNA-1273.529 as the first booster dose elicits a similar or superior antibody response to the B.1.1.529 compared to a single booster dose of mRNA-1273, using an external historical comparator. Study Part F Cohort 2 will assess whether a single booster dose of the mRNA-1273.529 as a second booster dose elicits a similar or superior antibody response to the B.1.1.529 compared to a single booster dose of mRNA-1273 as a second booster dose. Study Part G will assess whether a single booster dose of the mRNA-1273.214 as a second booster dose elicits a similar or superior antibody response to the B.1.1.529 compared to a single booster dose of mRNA-1273 as a second booster dose (Part F, Cohort 2, 50 µg mRNA-1273). Study Part A.2 will evaluate mRNA-1273.214 administered as a second booster dose to participants who rolled over from Part A.1. Study Part H will assess whether a

single booster dose of the mRNA-1273.222 50 µg as a second booster dose elicits a superior antibody response against Omicron BA.4/5 compared to a single booster dose of mRNA-1273 as a second booster dose (Part F, Cohort 2, 50 µg mRNA-1273). Part J will evaluate whether mRNA-1273.815 (50 µg) or mRNA-1273.231 (50 µg) administered as a booster will elicit antibody response against Omicron subvariants BA.4/BA.5, BQ.1.1, and XBB.1.5 in adults who previously received a primary series of mRNA vaccine, a first booster dose of a monovalent mRNA vaccine, and a second booster dose of a bivalent mRNA vaccine against SARS-CoV-2.

Table 2: Study Arm

Study Part	Study Arm	Dose ¹	N
Part A.1	mRNA-1273.211	50 µg	~300
	mRNA-1273.211	100 µg	~584
Part A.2 ²	mRNA-1273.214	50 µg	~300
Part B	mRNA-1273	100 µg	~300
Part C	mRNA-1273.617.2	50 µg	~584
	mRNA-1273.617.2	100 µg	~584
Part D	mRNA-1273.213	50 µg	~584
	mRNA-1273.213	100 µg	~584
Part E	mRNA-1273.213	100 µg	~50-100
Part F (Cohort 1)	mRNA-1273.529	50 µg	~375
Part F (Cohort 2)	mRNA-1273.529	50 µg	~375
	mRNA-1273	50 µg	~375
Part G	mRNA-1273.214	50 µg	~375
Part H	mRNA-1273.222	50 µg	~500
Part J (3 rd booster) ^{3, 4}	mRNA-1273.815	50 µg	~50
	mRNA-1273.231	50 µg	~50

¹ Dose is total mRNA.² Participants rolled over from Part A.1 to Part A.2.³ Participants may be rolled over from Part H.⁴ Participants will be randomized in a 1:1 ratio to receive either mRNA-1273.815 or mRNA-1273.231.

4.2. Statistical Hypotheses

Parts A.1, A.2, B, C, and D

There is no hypothesis testing for Parts A.1, A.2, B, C, and D.

Part E

There will be no formal hypothesis testing for Part E. All analyses will be descriptive.

Part F (Cohort 1)

50 µg mRNA-1273.529 as a first booster dose will be assessed with respect to mRNA-1273 as a first booster dose using mRNA-1273-P201 part B 50 µg booster after 100 µg primary series as an external comparator.

For the primary objective on immune response, hypotheses are:

- 50 µg mRNA-1273.529, as a single booster dose, against the variant B.1.1.529 is either non-inferior or superior to the booster dose of (50 µg) mRNA-1273 against B.1.1.529 based on the GMT ratio of mRNA-1273.529 against the variant B.1.1.529 at Day 29 compared to mRNA-1273 against the variant B.1.1.529 at Day 29 with a non-inferiority margin of 1.5.
- 50 µg mRNA-1273.529, as a single booster dose, against the variant B.1.1.529 is non-inferior to the booster dose of (50 µg) mRNA-1273 against B.1.1.529 based on the difference in SRR at Day 29 with a non-inferiority margin of 10%.

The primary immunogenicity objective is considered met if non-inferiority against B.1.1.529 (based on GMR and SRR difference) is demonstrated.

Part F (Cohort 2)

50 µg mRNA-1273.529 as a second booster dose will be compared to 50 µg mRNA-1273 as a second booster dose.

For the primary objective on immune response, hypotheses are:

- 50 µg mRNA-1273.529, as a second booster dose, against the variant B.1.1.529 is either non-inferior or superior to the second booster dose of (50 µg) mRNA-1273 against B.1.1.529 based on the GMT ratio of mRNA-1273.529 against the variant B.1.1.529 at Day 29 compared to mRNA-1273 against the variant B.1.1.529 at Day 29 with a non-inferiority margin of 1.5.

- 50 µg mRNA-1273.529, as a second booster dose, against the variant B.1.1.529 is non-inferior to the booster dose of (50 µg) mRNA-1273 against B.1.1.529 based on the difference in SRR at Day 29 with a non-inferiority margin of 10%.

The primary immunogenicity objective is considered met if non-inferiority against B.1.1.529 (based on GMR and SRR difference) is demonstrated.

[figure not shown]
Part G

50 µg mRNA-1273.214 as a second booster dose will be compared to 50 µg mRNA-1273 as the second booster dose (active control arm in Part F, Cohort 2, booster-to-booster comparison for the 2nd booster).

The primary objective on immune response will be tested with 0.025 two-sided alpha each initially allocated to Day 29 and Day 91 respectively. For the primary objective of immune response, an alpha of 0.05 (two-sided) will be allocated to the two time points. Day 29 and Day 91 will each have an alpha of 0.025 (two-sided) for hypotheses testing. If all objectives are met at Day 29, hypotheses at Day 91 can be tested at an alpha of 0.05 (two-sided).

[Figure 1](#) below demonstrates the testing strategy at Day 29 and Day 91.

Figure 1: Statistical Hypotheses Testing Strategy for Part G

Note: If all objectives are met at Day 29, hypotheses at Day 91 can be tested at an alpha of 0.05 (two-sided).

Hypotheses at Day 29:

- 50 µg mRNA-1273.214, as a second booster dose, against the variant B.1.1.529 is non-inferior to the second booster dose of (50 µg) mRNA-1273 against B.1.1.529 based on the GMT ratio of mRNA-1273.214 against the variant B.1.1.529 at Day 29 compared to mRNA-1273 against the variant B.1.1.529 at Day 29 with a non-inferiority margin of 1.5.
- 50 µg mRNA-1273.214, as a second booster dose, against the variant B.1.1.529 is non-inferior to the second booster dose of (50 µg) mRNA-1273 against B.1.1.529 based on the difference in SRR at Day 29 with a non-inferiority margin of 10%.
- 50 µg mRNA-1273.214, as a second booster dose, against the ancestral SARS-CoV-2 is non-inferior to the second booster dose of (50 µg) mRNA-1273 against the ancestral SARS-CoV-2 based on the GMT ratio of mRNA-1273.214 against the ancestral SARS-CoV-2 at Day 29 compared to mRNA-1273 against the ancestral SARS-CoV-2 at Day 29 with a non-inferiority margin of 1.5.
- 50 µg mRNA-1273.214, as a second booster dose, against the variant B.1.1.529 is superior to the second booster dose of (50 µg) mRNA-1273 against B.1.1.529 based on the GMT ratio of mRNA-1273.214 against the variant B.1.1.529 at Day 29 compared to mRNA-1273 against the variant B.1.1.529 at Day 29. Please note this hypothesis will only be tested when the above 3 hypotheses have been demonstrated.

Hypotheses at Day 91:

- 50 µg mRNA-1273.214, as a second booster dose, against the variant B.1.1.529 is non-inferior to the second booster dose of (50 µg) mRNA-1273 against B.1.1.529 based on the GMT ratio of mRNA-1273.214 against the variant B.1.1.529 at Day 91 compared to mRNA-1273 against the variant B.1.1.529 at Day 91 with a non-inferiority margin of 1.5.
- 50 µg mRNA-1273.214, as a second booster dose, against the variant B.1.1.529 is non-inferior to the second booster dose of (50 µg) mRNA-1273 against B.1.1.529 based on the difference in SRR at Day 91 with a non-inferiority margin of 10%.

- 50 µg mRNA-1273.214, as a second booster dose, against the ancestral SARS-CoV-2 is non-inferior to the second booster dose of (50 µg) mRNA-1273 against the ancestral SARS-CoV-2 based on the GMT ratio of mRNA-1273.214 against the ancestral SARS-CoV-2 at Day 91 compared to mRNA-1273 against the ancestral SARS-CoV-2 at Day 91 with a non-inferiority margin of 1.5.
- 50 µg mRNA-1273.214, as a second booster dose, against the variant B.1.1.529 is superior to the second booster dose of (50 µg) mRNA-1273 against B.1.1.529 based on the GMT ratio of mRNA-1273.214 against the variant B.1.1.529 at Day 91 compared to mRNA-1273 against the variant B.1.1.529 at Day 91. Please note this hypothesis will only be tested when the above 3 hypotheses have been demonstrated.

The primary immunogenicity objective is considered met if non-inferiority against B.1.1.529 based on GMR, SRR difference and non-inferiority against the ancestral SARS-CoV-2 based on GMR are demonstrated either at Day 29 or Day 91.

[figure not shown]
For the key secondary objective, hypotheses are (Day 29 and 91 will each have an alpha of 0.025 (two-sided) for hypotheses testing):

- 50 µg mRNA-1273.214, as a second booster dose, against the ancestral SARS-CoV-2 is non-inferior to the booster dose of (50 µg) mRNA-1273 against the ancestral SARS-CoV-2 based on the difference in SRR at Day 29 with a non-inferiority margin of 10%.
- 50 µg mRNA-1273.214, as a second booster dose, against the ancestral SARS-CoV-2 is non-inferior to the booster dose of (50 µg) mRNA-1273 against the ancestral SARS-CoV-2 based on the difference in SRR at Day 91 with a non-inferiority margin of 10%.

Part H

50 µg mRNA-1273.222 given as a second booster dose will be compared to 50 µg mRNA-1273 given as a second booster dose (in Part F, Cohort 2).

For the primary immunogenicity objective, there are 5 hypotheses to be tested. [Figure 2](#) below demonstrates the testing strategy.

Figure 2: Statistical Hypotheses Testing Strategy for Part H

For the primary immunogenicity objective, the 5 hypotheses to be tested are the following:

- 50 µg mRNA-1273.222, as a second booster dose, against Omicron BA.4/5 is non-inferior to the second booster dose of (50 µg) mRNA-1273 against Omicron BA.4/5 based on the GMT ratio of mRNA-1273.222 against Omicron BA.4/5 at Day 29 compared to mRNA-1273 against Omicron BA.4/5 at Day 29 with a non-inferiority margin of 1.5.
- 50 µg mRNA-1273.222, as a second booster dose, against Omicron BA.4/5 is non-inferior to the second booster dose of (50 µg) mRNA-1273 against Omicron BA.4/5 based on the difference in SRR at Day 29 with a non-inferiority margin, if
 - the lower bound of the 95% CI of the SRR difference (50 µg mRNA-1273.222 against Omicron BA.4/5 at Day 29 - 50 µg mRNA-1273 against Omicron BA.4/5 at Day 29) is >-5%, then the non-inferiority of mRNA-1273.222 against Omicron BA.4/5 compared to that of mRNA-1273 is demonstrated based on a non-inferiority margin of 5%.
 - the lower bound of the 95% CI of the SRR difference (50 µg mRNA-1273.222 against Omicron BA.4/5 at Day 29 - 50 µg mRNA-1273 against Omicron BA.4/5 at Day 29) is >-10% but \leq -5%, then non-inferiority of mRNA-1273.222 against Omicron BA.4/5 compared to that of mRNA-1273 is demonstrated based on a non-inferiority margin of 10%.

- 50 µg mRNA-1273.222, as a second booster dose, against the ancestral SARS-CoV-2 D614G is non-inferior to the second booster dose of (50 µg) mRNA-1273 against the ancestral SARS-CoV-2 D614G based on the GMT ratio of mRNA-1273.222 against the ancestral SARS-CoV-2 D614G at Day 29 compared to mRNA-1273 against the ancestral SARS-CoV-2 D614G at Day 29 with a non-inferiority margin of 1.5.
- 50 µg mRNA-1273.222, as a second booster dose, against the ancestral SARS-CoV-2 D614G is non-inferior to the second booster dose of (50 µg) mRNA-1273 against ancestral SARS-CoV-2 D614G based on the difference in SRR at Day 29 with a non-inferiority margin 10%.
- 50 µg mRNA-1273.222, as a second booster dose, against Omicron BA.4/5 is superior to the second booster dose of (50 µg) mRNA-1273 against Omicron BA.4/5 based on the GMT ratio of mRNA-1273.222 against Omicron BA.4/5 at Day 29 compared to mRNA-1273 against Omicron BA.4/5 at Day 29.

Part J

No formal hypothesis testing will be performed for Part J and all safety and immunogenicity analyses will be descriptive.

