- F. H_1^6 : 50 μ g mRNA-1273.214, as a second booster dose, against the variant B.1.1.529 is non-inferior to the second booster dose of (50 μ g) mRNA-1273 against B.1.1.529 based on the difference in SRR at Day 91 with a non-inferiority margin of 10%.
- G. H_1^7 : 50 μ g mRNA-1273.214, as a second booster dose, against ancestral SARS-CoV-2 is non-inferior to the second booster dose of (50 μ g) mRNA-1273 against ancestral SARS-CoV-2 based on the GMT ratio of mRNA-1273.214 against ancestral SARS-CoV-2 at Day 91 compared to mRNA-1273 against ancestral SARS-CoV-2 at Day 91 with a non-inferiority margin of 1.5
- H. H_1^8 : 50 μ g mRNA-1273.214, as a second booster dose, against the variant B.1.1.529 is superior to the second booster dose of (50 μ g) mRNA-1273 against B.1.1.529 based on the GMT ratio of mRNA-1273.214 against the variant B.1.1.529 at Day 91 compared to mRNA-1273 against the variant B.1.1.529 at Day 91.

For the primary immunogenicity objective, an alpha of 0.05 (two-sided) will be allocated to the 2 time points (Day 29 and Day 91). Day 29 and Day 91 will each have an alpha of 0.025 (two-sided) for hypotheses testing.

The primary immunogenicity objective is considered met if non-inferiority against B.1.1.529 based on GMR, SRR difference, and non-inferiority against ancestral SARS-CoV-2 based on GMR are demonstrated at Day 29 or Day 91.

For the key secondary immunogenicity objective, there are 2 hypotheses to be tested (Day 29 and Day 91 will each have alpha of 0.025 [two-sided] for hypotheses testing):

- A. H_1^9 : 50 μ g mRNA-1273.214, as a second booster dose, against ancestral SARS-CoV-2 is non-inferior to the booster dose of (50 μ g) mRNA-1273 against ancestral SARS-CoV-2 based on the difference in SRR at Day 29 with a non-inferiority margin of 10%.
- B. H_1^{10} : 50 μ g mRNA-1273.214, as a second booster dose, against ancestral SARS-CoV-2 is non-inferior to the booster dose of (50 μ g) mRNA-1273 against ancestral SARS-CoV-2 based on the difference in SRR at Day 91 with a non-inferiority margin of 10%.

Part H:

50 μ g mRNA-1273.222 given as a second booster dose will be compared to 50 μ g mRNA-1273 given as a second booster dose (in Part F, Cohort 2).

For the primary immunogenicity objective, there are 5 hypotheses to be tested as shown in [Figure 2](#):

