Hypotheses testing at Day 91 will be performed in the same manner, first test 2 non-inferiority hypotheses (2 against the B.1.1.529 strain and one against ancestral SARS-CoV-2) at alpha of 0.025 level (two-sided). Once non-inferiority is demonstrated for both B.1.1.529 and ancestral SARS-CoV-2, then superiority testing against the B.1.1.529 at alpha of 0.025 level (two-sided) will be performed.

For the key secondary objective, there are 2 hypotheses to be tested (Day 29 and Day 91 each with alpha level of 0.025, 2-sided):

- A. H_1^9 : 50 µg mRNA-1273.214, as a second booster dose, against ancestral SARS-CoV-2 is non-inferior to the booster dose of (50 µg) mRNA-1273 against ancestral SARS-CoV-2 based on the difference in SRR at Day 29 with a non-inferiority margin of 10%.
- B. H_1^{10} : 50 µg mRNA-1273.214, as a second booster dose, against ancestral SARS-CoV-2 is non-inferior to the booster dose of (50 µg) mRNA-1273 against ancestral SARS-CoV-2 based on the difference in SRR at Day 91 with a non-inferiority margin of 10%.

If the lower bound of the 97.5% CI of the SRR difference (50 µg mRNA-1273.214 against ancestral SARS-CoV-2— 50 µg mRNA-1273 against ancestral SARS-CoV-2) is >-10% at Day 29 or Day 91, then the key secondary objective will be considered met.

In the event that an early assessment of the 1273.214 data is needed due to public health concerns, a two-staged approach will be used. Specifically, a subset of participants' (ie, 50 first enrolled participants) serum samples will first be tested against ancestral SARS-CoV-2 and various VOCs. For the Day 29 and Day 91 immunogenicity analyses, all participants' immune data will be used in the formal analysis to evaluate the primary immunogenicity objective.

[figure not shown]

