
- If non-inferiority is demonstrated for both B.1.1.529 (based on GMR and SRR) and ancestral SARS-CoV-2 (based on GMR), the lower bound of 97.5% CI of GMR will be compared to 1, if it's greater than 1, then superiority against B.1.1.529 is demonstrated.

Analyses for the primary immunogenicity endpoints may also be performed using Per-Protocol Immunogenicity Set.

Day 91: alpha=0.025 (2-sided)

Hypotheses testing at Day 91 will be performed in the same manner, first test two non-inferiority hypotheses (two against the B.1.1.529 strain and one against ancestral SARS-CoV-2) at alpha of 0.025 level (two-sided). Once non-inferiority is demonstrated for both B.1.1.529 and ancestral SARS-CoV-2, then superiority testing against the B.1.1.529 at alpha of 0.025 level (two-sided) will be performed.

For the key secondary objective, hypotheses to be tested (Day 29 and Day 91 each with alpha level of 0.025, 2-sided) are described in [Section 4.2](#). If the lower bound of the 97.5% CI of the SRR difference (50 µg mRNA-1273.214 against the ancestral SARS-CoV-2 - 50 µg mRNA-1273 against ancestral SARS-CoV-2) is >-10% at Day 29 or Day 91, then key secondary objective will be considered met.

In the event that an early assessment of the 1273.214 data is needed due to public health concerns, a two-staged approach will be used. Specifically, a subset of participants' (ie, 50 first enrolled participants) serum samples will first be tested against ancestral SARS-CoV-2 and various VOCs. For the Day 29 and Day 91 immunogenicity analyses, all participants' immune data will be used in the formal analysis to evaluate the primary immunogenicity objective.

Part H

Primary analysis set for immunogenicity objectives will be based on PPIS-Neg.

50 µg mRNA-1273.222 as the second booster dose will be compared to 50 µg mRNA-1273 as the second booster dose (active control arm in Part F, Cohort 2).

Study Part H was enrolled in August 2022 and Part F 50 µg mRNA-1273 was enrolled in February 2022, baseline and demographic characteristics will be examined between the two study parts before comparing immunogenicity data.

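### Part G, Day 91: SAP 4.2 raises the test level to 0.05 after Day 29 success, while SAP 6.4.3 keeps it at 0.025 without condition

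*SAP*

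**What the plan says.** SAP Section 4.2 describes the Part G primary tests as having "0.025 two-sided alpha each initially allocated to Day 29 and Day 91 respectively". It then allows a higher level at Day 91: "If all objectives are met at Day 29, hypotheses at Day 91 can be tested at an alpha of 0.05 (two-sided". The printed note under the SAP's Figure 1 repeats that step.

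SAP Section 6.4.3 turns the hypotheses into decision rules. It heads the later block "Day 91: alpha=0.025 (2-sided". It places the Day 91 non-inferiority tests ("two against the B.1.1.529 strain and one against ancestral SARS-CoV-2) at alpha of 0.025 level (two-sided") at that level, and continues: "then superiority testing against the B.1.1.529 at alpha of 0.025 level (two-sided) will be performed". No condition on Day 29 appears there. Section 6.4.3 does point the reader to Section 4.2 for the hypotheses.

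Protocol Section 8.2 says: "Day 29 and Day 91 will each have an alpha of 0.025 (two-sided) for hypotheses". Protocol Section 8.5.3.1.4 repeats 0.025 for Day 91, including "then superiority testing against the B.1.1.529 at alpha of 0.025 level (two-sided". The readable protocol text contains no step to 0.05. Neither document's Figure 1 is shown in the material available for review, apart from the SAP note.

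**The concern.** The two SAP sections agree when Day 29 fails: Day 91 is then tested at 0.025 under both. They part when Day 29 succeeds. Section 4.2 then permits 0.05 (a 95% confidence interval), while Section 6.4.3 prescribes 0.025 (a 97.5% interval). The precedence clause in the SAP's Introduction ranks the SAP over the protocol. It does not rank one SAP section over another.

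At stake are the separate Day 91 claims. SAP Section 2.1 lists superiority against B.1.1.529 at Day 91 among the Part G primary objectives. An observed result that falls between the two cut-offs would be a success by one page of the SAP and a failure by another, and the choice of interval would be open after the data are seen.

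**Working it through.** **Inputs** (SAP 4.3, Part G): 300 evaluable per arm; SD of log titer 1.5, taken on the natural-log scale; true GMR 1.5 against B.1.1.529 and 1 against ancestral virus; GMR margin 1.5; true SRR 90% in both arms; SRR margin 10 points; stated global power about 71% at 0.025 two-sided.

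**Step 1. Reproduce the stated power.** SE of log GMR = 1.5 × √(2/300) = 0.1225. SE of the SRR difference = √(2 × 0.9 × 0.1/300) = 0.0245. The critical value is 2.241 at 0.025 and 1.960 at 0.05.

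| Test | Power at 0.025 | Power at 0.05 |
|---|---|---|
| Non-inferiority GMR, B.1.1.529 | >0.999 | >0.999 |
| Non-inferiority SRR, B.1.1.529 | 0.967 | 0.983 |
| Non-inferiority GMR, ancestral | 0.858 | 0.912 |
| Superiority GMR, B.1.1.529 | 0.858 | 0.912 |
| All four, taken as independent | 0.711 | 0.817 |

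The 71% reproduces at 0.025 with superiority included; the three non-inferiority tests alone give 0.829. Since 0.025 is the starting level under both sections, the 71% does not show which Day 91 rule was intended.

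**Step 2. Observed Day 91 values needed.**
- Superiority: exp(2.241 × 0.1225) = 1.316 at 0.025; exp(1.960 × 0.1225) = 1.271 at 0.05.
- Ancestral non-inferiority: exp(−ln 1.5 + z × 0.1225) = 0.877 at 0.025; 0.848 at 0.05.
- SRR difference, Wald approximation: −10 + 2.241 × 2.45 = −4.5 points; −10 + 1.960 × 2.45 = −5.2 points.
- SRR, unstratified Miettinen-Nurminen score with 270/300 control responders: 256 responders give 1.949, 257 give 2.078, 258 give 2.208 and 259 give 2.338. So 257 and 258 pass at 0.05 only. The SAP stratifies by age group and gives no strata sizes, so this is an approximation.

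**Step 3. Sensitivity of the superiority cut-offs.**
- If 1.5 is the unadjusted SD and the ANCOVA baseline titer has correlation r with the outcome (assumed), SE is multiplied by √(1 − r²). This gives 1.268 versus 1.231 at r = 0.5, and 1.217 versus 1.187 at r = 0.7.
- SAP 4.3 plans 260 evaluable in this same control arm for Part H. With 300 versus 260, the cut-offs are 1.330 versus 1.283.

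**Step 4. How often the verdict on the whole Day 91 chain changes.** With the two days independent, P(Day 29 fully met) × (0.817 − 0.711) = 0.711 × 0.106 = 0.075. Simulation (4 million draws, endpoints independent within a day) gives 6.5% at a Day 29/Day 91 correlation of 0.5 and 4.8% at 0.9. The documents give no such correlation; these values are assumed.

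**Step 5. Error rate under recycling.** When the nulls for both days hold, the extra alpha is available only after a Day 29 rejection, so it cannot create a first false rejection. With one test per day, simulated two-sided error is 0.049 at correlation 0 and 0.036 at 0.9. It is about 0.050 when only the Day 91 null is true. When all four Day 29 hypotheses must be met and the non-inferiority tests all pass, one-sided error is 0.0248 with both superiority nulls true and 0.0250 with only the Day 91 null true.

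**The case against.** The best defence is that 6.4.3 only repeats the starting level. It cross-refers to 4.2 for the hypotheses. In 4.2 itself, an equally flat statement of 0.025 for each day comes just before the recycling sentence. On this reading the SAP uses unconditional wording for the initial level, and 4.2 with its figure note holds the full strategy. The defect would then be a conditional clause that was not carried over. That is plausible and may be what was intended. It does not remove the problem, because the cross-reference is to the hypotheses, and 6.4.3 then sets its own Day 91 level in mandatory terms while 4.2 uses permissive ones.

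It is also fair to say that the protocol's Figure 1 is not visible, so it cannot be said that the whole protocol lacks the step. Nor does the SAP's figure settle the matter, since its note repeats the 0.05 step and leaves 6.4.3 unchanged.

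A reader might go further and infer that recycling inflates the error rate, on the view that the three non-inferiority tests alone release the Day 29 alpha. The documents do not support this. SAP 2.1 lists superiority among the Part G primary objectives, and 4.2 lists it as the fourth Day 29 hypothesis, so the natural reading of the release condition includes it. The 4.2 rule for when the primary immunogenicity objective counts as met is a different statement. A reader might also look for inflation from the key secondary test. Its place in the testing order may be shown in the figures, and it is a separate matter from the 4.2/6.4.3 conflict.

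**Conclusion.** The Day 91 decision level for Part G is contradictory as written and should be reconciled. The conflict arises only after all Day 29 objectives are met.

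It would be wrong to conclude that the overall primary objective is at risk. SAP 4.2 counts it as met on the non-inferiority set at either day, and 0.05 comes into play only after Day 29 has succeeded. With release tied to all four Day 29 hypotheses, the recycling is also valid for the primary tests. This is therefore an inconsistency in level and interval width, with no demonstrated inflation.

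What can change is a separate Day 91 claim whose result falls in a narrow band: an observed superiority GMR between 1.271 and 1.316, or an ancestral GMR between 0.848 and 0.877. Across the full chain this is about 5 to 7.5% of trials. These sizes rest on the planning figures of 300 per arm and log SD 1.5, on independent endpoints, and on assumed correlations between the days. A smaller control arm or a useful baseline covariate shifts the band but does not remove it.

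**What to change.** State one Day 91 rule, in the same terms, in SAP 4.2 and 6.4.3, and align the protocol. SAP 6.4.1 lists the Part G Day 91 assays as tested, so the rule should not be chosen now on its merits. Keep the rule that was in force when Day 91 was first analysed, and record that it was.

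- If that rule was a fixed 0.025: delete the recycling sentence and the Figure 1 note in SAP 4.2.
- If it was recycling: add to the Day 91 block of 6.4.3 that if all four Day 29 primary hypotheses (three non-inferiority and superiority) are met, Day 91 is tested at 0.05 (95% CI), and otherwise at 0.025 (97.5% CI). Use the same release condition in 4.2, and carry the step into the protocol. Protocol Section 8 calls for an amendment when methods for primary objectives change.

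The cost is wording only. Under the planning assumptions, Day 91 full-chain power is 71% at fixed 0.025 and about 76 to 79% with recycling (at correlation 0: 0.711 × 0.817 + 0.289 × 0.711 = 0.786). The fixed rule therefore gives up roughly 5 to 7.5 points. The stated 71% can stand under either rule.
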